# Descriptive Summary statistics will be conducted for the following:

# Cohorts 1 and 2:

• Patient HCRU (hospitalization and LOS, ICU admission and LOS, supplemental oxygen use and type, outpatient visits, and ER visits

Exploratory stratifications will be conducted, as appropriate and where the sample size permits, to explore differences by:

• Age groups: 18–29, 30–49, 50–64, 65–74, ≥75 years of age;

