#### 4.2 SUBGROUPS

*Exploratory stratifications will be conducted, as appropriate and where the sample size permits, to explore differences by:* 

- *Age groups: 18–49, 50–64, 65–74, ≥75 years of age;*
- Gender;
- *BMI categories:* (<18.5 = underweight, 18.5−24.9 = normal, 25−29.9 = overweight, ≥30 = obese);
- *Smoking status;*
- *Medications used to treat COVID-19 in addition to nirmatrelvir, ritonavir;*
- *Previous COVID-19 infection;*
- COVID-19 vaccination history;
- *Nirmatrelvir, ritonavir treatment completion (if available)*
- Days from COVID-19 diagnosis to nirmatrelvir, ritonavir index date;
- Days from prescription to dispensing (if available).
- Days from COVID 19 symptoms onset to dispensing (if available).
- Days from COVID 19 symptoms onset to nirmatrelvir, ritonavir prescription (if available).

For each stratification variable, the full analysis set will be segmented into nonoverlapping subgroups based on the stratification variable values. The stratifications may not be meaningful, if there are no patient's data in some of the groups or there are many variables with a lot of missing data.

The exploratory stratifications will be conducted for the following study objectives if enough data are available:

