# Secondary objective: To assess adult COVID-19 patients' HCRU within the 30-day period following nirmatrelvir, ritonavir prescription, including: Overall HCRU in inpatient and outpatient settings.

The specific stratifications, and their corresponding reporting labels will be the following:

• Age groups: Age at time of PAXLOVID™ prescription will be further categorized into 18–49, 50–64, 65–74, ≥75 years. Descriptive summary tables for subgroup analysis by defined age groups for the specified study objectives will be created as shown in *Table Shells 10*.

PFIZER CONFIDENTIAL CT24-WI-GL03-RF03 2.0 Non-Interventional Statistical Analysis Plan 01-Jun-2020 Page 14 of 42 *Gender (Male, Female);* Descriptive summary tables for subgroup analysis by gender for the specified study objectives will be created as shown in *Table Shells* 11

- *BMI categories:* Body Mass Index (BMI) at time of PAXLOVID™ prescription will be further categorized as <18.5 = underweight, 18.5–24.9 = normal, 25–29.9 = overweight, ≥30 = obese. Descriptive summary tables for subgroup analysis by defined BMI categorization for the specified study objectives will be reported as shown in *Table Shells 12*.
- *Smoking status (*Never smoker; Former smoker; Current smoker); Descriptive summary tables for subgroup analysis by smoking status in terms of never smoker, former smoker and current smoker for the specified study objectives will be reported as shown in *Table Shells 13*.
- Medications used to treat COVID-19 in addition to nirmatrelvir, ritonavir; Descriptive summary tables for subgroup analysis by Medications used to treat COVID-19 in addition to nirmatrelvir, ritonavir at time of PAXLOVIDTM prescription for the specified study objectives will be reported as shown in *Table Shells 14.*
- *Previous COVID-19 infection (Yes, No);* Descriptive summary tables for subgroup analysis by Previous COVID-19 infection for the specified study objectives will be created as shown in *Table Shells 15.* Additionally, Number of previous COVID-19 infections before the index date will be reported and further stratified by 0, 1, 2 and more. Descriptive summary tables for these groups will be reported as shown in *Table Shell 15.1* (If sufficient data available).
- *COVID-19 vaccination history;* Descriptive summary tables for subgroup analysis by COVID-19 vaccination history for the specified study objectives will be reported as shown in *Table Shells 16.*

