#### Statistical analysis description

## 1. "Stratified analysis of Paxlovid prescription at index by demographic and clinical characteristics"

Data related to Nirmatrelvir/Ritonavir prescription in terms of specialty of provider total dose of Nirmatrelvir/Ritonavir, in case of "other" dose specified of Nirmatrelvir and Ritonavir, frequency, dispensed amount, type dispensed, days from COVID-19 diagnosis to nirmatrelvir, ritonavir at index date, days from prescription to dispensing days from COVID-19 symptoms onset to dispensing and days from COVID-19 symptoms onset to nirmatrelvir, ritonavir prescription will be summarized in descriptive statistics by:

- Age groups: 18–49, 50–64, 65–74, ≥75 years
- Gender
- BMI categories:  $(<18.5 = underweight, 18.5-24.9 = normal, 25-29.9 = overweight, \geq 30 = obese).$
- Smoking status.
- Previous COVID-19 infection.
- COVID-19 vaccination history.

These tables will be reported as shown in the table shells 7.1 to 7.6

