## 3. "Examine the relationship between patients' hospitalization due to COVID-19 related reasons and various demographic and clinical factors at the index date."

We will be utilizing both univariate and multivariate binomial logistic regression to examine the association between patients' hospitalization due to COVID-19 at the index date and demographic and clinical factors mentioned below (covariates). All p-values will be reported as two-sided, and statistical significance will be determined at 0.05 alpha level. Separate univariate binary logistic regression model will be conducted for each covariate listed below and only covariates which will be found significant will be included in the Multivariate model along with clinically significant covariates (e.g BMI, Previous comorbidity status etc.). No interaction terms will be included in the model.

The following binary logistic regression equation will be used to model the relationship:

 $log(odds) = \beta_0 + \beta_1 X_1 + \beta_2 X_2 + \dots + \beta_n * X_n$ 

Where:

- log(odds) represents the logarithm of the odds of the patients' hospitalization due to COVID-19
- $\beta_0$  is the intercept or constant term.
- β1, β2, ..., βn are the coefficients associated with the independent variables (covariates) X1, X2, ..., Xn.
- X1, X2, ..., Xn are the values of the independent variables (Covariates)

Here,

**Outcome variable (Dependent variable):** patients' hospitalization due to COVID-19 related at index date (Yes=1/No\*\*=0).

\*\*No: No will include both "patients who had no hospitalization" as well as "patients with hospitalization due to non-COVID-19 related reasons".

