#### **Covariates (Independent variables):**

- Age groups (Reference group: 18-29 Year)
- Gender (Reference group: Female)
- BMI categories (Reference group: Normal)
- Smoking status (Reference group: Never smoke)
- Pre-existing comorbidities (Yes/No, Reference group: No)
- Previous COVID-19 infection (Yes/No, Reference group: No)
- COVID-19 vaccination history (Yes/No, Reference group: No)

The results will be presented in the terms of odd ratio (by exponentiating the logistic regression coefficient) and corresponding 95% CI. "p-values" and "confidence intervals (CIs)" will be obtained using statistical methods such as maximum likelihood estimation (MLE) or Wald tests.

These tables will be reported as shown in the table shells 24 to 24.1.

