#### 11 APPENDICES

#### 11.1 ANNEX 1 (TABLE 2): STUDY VARIABLES AND DEFINITIONS

Variables	Role	Time point(s)	Operational definition
Age, Continuous	Patient demographics (Primary endpoint)	At index date	Age will be reported in year
Age, Category	Stratification variable	At index date	The age (Year) will be categorized as: • 18-49 Years • 50-64 Years • 65-74 Years • >75 Years
Gender	Patient demographics (Primary endpoint)	At index date	Gender (Sex) will be reported as: • Male • Female
Ethnicity	Patient demographics (Primary endpoint)	At index date	Ethnicity will be reported as: • Arab • Afro-Asian • Asian/Pacific Islander • Black/African American • Hispanic/Latino • Native American/Alaskan Native • White/Caucasian, • Multiracial/Biracial • Unknown. • Other [specify]
Education	Patient demographics (Primary endpoint)	At index date	Education will be reported as: No formal education Primary school Secondary school Undergraduate university degree Master's degree PhD or doctorate
Employment status	Patient demographics (Primary endpoint)	At index date	Employment status will be reported as: • Full-time employment • Part-time employment • Homemaker • Student • Retired • Disabled/too ill to work • Unemployed

PFIZER CONFIDENTIAL CT24-WI-GL03-RF03 2.0 Non-Interventional Statistical Analysis Plan 01-Jun-2020 Page 32 of 42

Variables	Role	Time point(s)	Operational definition
Weight (kg)	Patient clinical characteristics (Primary endpoint)	At index date	Weight will be reported in kilograms (kg)
Height (m)	Patient clinical characteristics (Primary endpoint)	At index date	Height will be reported in meters (m)
BMI (kg/m  )	Patient clinical characteristics (Primary endpoint)	At index date	BMI will be calculated automatically based on the reported weight and height in the unit of kilograms over squared meters (kg/m  ).
BMI category	Stratification variable	At index date	The calculated BMI will be categorized as: • Underweight (< 18.5) • Normal (18.5–24.9) • Overweight (25–29.9) • Obese (≥30)
Smoking Status	Patient clinical characteristics (Primary endpoint)	At index date	Smoking status will be reported as: • Never smoker • Former smoker • Current smoker
Pre-existing comorbidities	Patient clinical characteristics (Primary endpoint)	At index date	Pre-existing comorbidities will be reported as: • No • Yes If yes, will be specified as: • Diagnosis

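### SAP 7.3 logistic model: the age reference band is not a level of the SAP's age variable, the adjusted odds ratios are reported selectively, and the 0.05 rule conflicts with 7.1

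*SAP*

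**What the plan says.** **Age.** The covariate list in SAP 7.3 item 3 gives "Age groups (Reference group: 18-29 Year". SAP 4.2 defines "Age groups: 18–49, 50–64, 65–74, ≥75 years of age" and repeats in its reporting labels that age "will be further categorized into 18–49, 50–64, 65–74, ≥75 years". Items 1 and 2 of section 7.3 use the same four bands (item 1: "Age groups: 18–49, 50–64, 65–74, ≥75 years"). Annex 1 (Table 2) also starts at 18-49: "The age (Year) will be categorized as: • 18-49 Years". Protocol 9.8.2 has five bands: "Age groups: 18–29, 30–49, 50–64, 65–74, ≥75 years of age".

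**Covariates.** Item 3 lists seven candidates: age, gender, BMI, smoking, comorbidity, previous infection and vaccination. Each gets its own univariate model, and "only covariates which will be found significant will be included in the Multivariate model". Covariates judged clinically significant are added, but these are given only as examples (BMI, previous comorbidity) ending in an et cetera.

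**Testing and method.** Item 3 sets two-sided significance at 0.05. SAP 7.1, like protocol 9.8, says the study is descriptive and no tests will be done; neither exempts 7.3. P-values and intervals "will be obtained using statistical methods such as maximum likelihood estimation (MLE) or Wald tests".

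**Status.** Section 7.3 is headed as exploratory. The version 2.0 entry in the SAP amendment table discloses that analyses already performed influenced it.

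**The concern.** A reference category must be a level of the variable. A programmer who reaches item 3 must either move the reference to 18-49 or rebuild the protocol's five bands from age in years. Both are feasible and nothing in the SAP chooses between them. They give different age odds ratios unless risk is flat below 50, and different precision even then.

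The screen decides which adjusted odds ratios appear in shell 24.1. Those shown because they passed at 0.05 are on average too far from 1, and their intervals ignore the selection. The adjustment set is also unsettled, because the forced-in covariates are only exemplified. Item 3 does not say whether a multi-level covariate is screened by one overall test or coefficient by coefficient.

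This is the only inferential model in the plan, and its odds ratios are likely to be read as risk factors for hospitalization. Because the section was written after results had been seen, open choices of reference and covariates matter more than they would in a plan fixed beforehand.

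**Working it through.** The documents state no event rate, effect size or power for this model, so there is no figure to reproduce. N = 250 is the SAP's minimum target. All other inputs below are assumptions.

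**1. Is 18-29 a level?** SAP bands: 18-49, 50-64, 65-74, ≥75: no. Protocol bands: 18-29, 30-49, 50-64, 65-74, ≥75: yes.

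**2. Effect of the reference on the odds ratio.** Assume risk 30% at ≥75 and 10% at 30-49, with 35% of patients aged 18-49 and 5-15% of all patients aged 18-29. With risk 5% at 18-29:
- Against 18-29: (0.30/0.70)/(0.05/0.95) = 8.14.
- Against 18-49: the pooled risk is (5/35)(0.05) + (30/35)(0.10) = 0.0929, or (15/35)(0.05) + (20/35)(0.10) = 0.0786, giving odds ratios of 4.2 and 5.0.

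| Risk at 18-29 | ≥75 vs 18-29 | ≥75 vs 18-49 |
|---|---|---|
| 10% | 3.9 | 3.9 |
| 8% | 4.9 | 4.0-4.3 |
| 5% | 8.1 | 4.2-5.0 |

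**3. Effect on precision when risk is flat at 10% below 50.** Take 38 patients aged ≥75 (15% of 250) and n in the reference band. SE = √[1/(n×0.1×0.9) + 1/(38×0.3×0.7)]; the upper/lower ratio of the 95% interval is exp(2×1.96×SE); the chance of no event in the reference band is 0.9ⁿ.

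| Reference | n | Upper/lower ratio | Chance of no event |
|---|---|---|---|
| 18-29 at 5% of patients | 13 | 48.5 | 25% |
| 18-29 at 15% of patients | 38 | 12.6 | 1.8% |
| 18-49 at 35% of patients | 88 | 7.1 | 0.01% |

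**4. Model size.** With four age bands: 3 + 1 (gender) + 3 (BMI) + 2 (smoking) + 1 + 1 + 1 = 12 coefficients; with five bands, 13. At 10/20/30% event rates, 250 patients give 25/50/75 events, or 2.1/4.2/6.3 per coefficient with 12.

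**5. The screen under no association.** Seven independent screens at 0.05: 1 − 0.95⁷ = 30.2% chance of at least one false selection.

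**6. The screen with a true effect.** This was simulated at N = 250 with 6,000 datasets per setting. Gender (50:50) carried a true odds ratio of 1.5 and the other covariates were null and independent. Assumed distributions: age 35/30/20/15%, BMI 5/25/30/40%, smoking 70/15/15%, comorbidity 60%, previous infection 15%, vaccination 80%. BMI and comorbidity were forced in. Non-converged screened fits were dropped.

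| Reference-group risk | 10% | 20% | 30% |
|---|---|---|---|
| Gender passes the screen | 17% | 27% | 33% |
| Screened model, median OR when it passes | 2.74 | 2.15 | 2.00 |
| Its 95% interval coverage | 84% | 90% | 91% |
| Unscreened Firth model, same passing datasets (two runs) | 2.58-2.65 | 2.09-2.12 | 1.95-1.97 |
| Unscreened Firth model, all datasets | 1.49 | 1.50 | 1.52 |

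Rows two and four are the like-for-like pair, and they nearly agree. The distance between rows four and five comes from looking only at datasets where gender was significant. For a true odds ratio of 2.0 the screened medians are 2.75/2.33/2.22 with coverage of 95-96%, so the distortion shrinks as the effect grows. A forced-in covariate is not inflated: comorbidity came out at 1.51-1.54 for a true 1.5.

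**The case against.** The strongest reply is that this is editorial. The candidate list is closed at seven, the section is labelled exploratory, the influence of earlier analyses is disclosed, and shell 24 still prints every crude odds ratio. The sentence ruling out tests was carried over from the protocol, which lets the SAP modify its plans, so one line exempting 7.3 would remove the conflict. Maximum likelihood and Wald are not rival methods: one is an estimator and the other a test and interval built on it.

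Much of that stands. A reader might infer from the simulation that removing the screen would turn an odds ratio of 2.74 into 1.5. It would not: in a given dataset the unscreened model prints nearly the same value for a covariate that passed. A reader might also infer that the documents require a Firth fit, complete cases or deletion of all p-values. They do not. No event count is given, so sparsity is not shown. SAP section 6 says missing data do not exclude patients, and with 2/5/10% missing independently in six covariates, complete cases would leave 250 × (1 − m)⁶ = 221/184/133. An exemption in 7.1 would reconcile the testing language as well as deletion would.

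The simulation has limits too: its covariates are independent with a single true effect, so it says nothing about confounders lost through screening. The table shells sit in a separate spreadsheet that is not reproduced, so the age bands used in shells 24 and 24.1 cannot be checked.

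None of this answers the age reference, which no SAP age grouping contains, or the selective content of shell 24.1.

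**Conclusion.** The point holds and should be fixed before the model is run or reported. The age reference is wrong as written on the SAP's own variable. The choice of repair could leave the oldest-band odds ratio unchanged at 3.9 (flat risk below 50) or move it between 8.1 and 4.2-5.0 (risk halved at 18-29). Interval ratios are about 13 to 49 against 18-29, compared with 7 against 18-49.

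The screen's harm is selective reporting and an adjustment set that is not fixed; it does not produce a materially different estimate from the same data. The gain from dropping it is that all seven adjusted odds ratios appear whatever their significance. The conflict between 7.1 and 7.3 is literal and easily settled.

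A reader might take this as a threat to the study's main results. The documents do not support that: the primary and secondary objectives are descriptive and do not use this model. All sizes depend on the assumed event rates, age mix and covariate distributions.

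**What to change.** - **SAP 7.3, covariate list:** set the age reference to 18-49.
- **SAP 7.3 item 3:** delete the univariate screen and the open-ended clause on clinically significant covariates. Fit one model with the seven listed covariates (12 coefficients). Keep the crude odds ratios in shell 24 as description.
- **SAP 7.1 and 7.3:** either drop the 0.05 rule and report odds ratios with 95% intervals, or add a sentence to 7.1 exempting the exploratory section.
- **Useful clarifications:** name the interval method, say how missing covariate values enter the model, and report the model's n. Complete cases should not be imposed against section 6.
- **Keep the amendment-table disclosure with the results.** Closing the covariate list now does not make it prespecified.

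The cost is a few lines of SAP text and no new data. Some intervals widen slightly. In the simulation at true odds ratio 1.5, the upper/lower ratio for a forced-in covariate at 10/20/30% risk was 4.89/3.50/3.08 with an unscreened Firth fit and 5.12/3.46/3.00 with the screened model, so at most about 3% wider. These are Wald widths, and the unscreened maximum likelihood width was not computed. If events are few, the larger model may fail to converge: 26/6/1% of maximum likelihood fits failed, against 22/5/1% with the screen. A Firth fit, which converged in every dataset at N = 250, is an option in that case and not a requirement.

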#### 9.6. Study Size

This is an observational study without any pre-defined hypothesis to be tested; rather, it addresses descriptive objectives. As such, power calculations are not applicable. However, based on feasibility assessments, a planned minimum total sample size of 500 patients for this study will ensure adequate exploration of the study objectives, and sufficient generalizability of findings.

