#### Limitations

Since this study will involve collection of existing data from medical records, misclassification bias due to recording errors is possible. Medical records may not always be complete, the availability and quality/completeness of data may vary considerably between different sites within KSA, and there may be abstraction errors and differences in reporting standards between the different sites. Another limitation to be considered is the characteristics of the patient population to be included in the final analysis, which may potentially be biased based on the KSA national recommendations put in place for the management and treatment of COVID-19 during the observational period. This may affect the generalizability of findings from this study across different countries in the real-world setting.

At the patient-level, misclassification of drug exposure has to be considered. Medical records provide detailed information on patient demographics, clinical characteristics, and prescribed nirmatrelvir, ritonavir treatment, but may not contain information on the intended duration of use (days of supply) and may not contain accurate information on the actual treatment pattern of nirmatrelvir, ritonavir medications by the patient ie, patient adherence (if any).

COVID-19 outcomes are dependent on individuals seeking healthcare (ie, individual may have symptoms for long but if there is not an interaction with the health system, it will be unknown.

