#### 3.1 STUDY DESIGN

This is a multi-center, retrospective observational study that will be conducted in KSA. The aim of this study is to capture data on the baseline demographic, clinical characteristics, and HCRU of adult COVID-19 patients who have been prescribed nirmatrelvir, ritonavir treatment.

An overview of the study design is depicted in Figure 1. The sample size for this study depends on the number of COVID-19 patients visiting the selected sites, in addition to nirmatrelvir, ritonavir prescription practices by the treating physician in line with local prescription guidelines in KSA. However, based on feasibility assessments, the minimum target sample size for the study is approximately 250 evaluable patients across 3 sites in KSA. The study will aim to meet this target sample size with a single Cohort of patients identified retrospectively prior to the date of site initiation (Cohort 1); however, if the target sample size is not met, then a second Cohort of patients will be initiated after the site initiation date (Cohort 2).

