#### Figure 1. Study Design

#### 3.1.1 Study population

Data will be collected for all eligible adult COVID-19 patients who have been prescribed nirmatrelvir, ritonavir across 3 selected sites in KSA which are National Guard Hospital-Riyadh, King Faisal Specialist Hospital-Riyadh and King Faisal Specialist Hospital-Jeddah. These 3 healthcare centers are the largest COVID-19 care providers in KSA representing the majority of COVID-19 patients who have been prescribed nirmatrelvir, ritonavir at the national level. In addition, these three healthcare centers have the same guidelines for treatment and management of patients with COVID-19.

The selected sites with well-established clinical research infrastructures, are situated in the major cities of KSA, where COVID-19 patients are most prevalent. They provide medical attention to any COVID-19 patient and provide healthcare to complicated patients, including immunocompromised patients.

These facilities also maintain patient records and have access to electronic medical records for patient data retrieval.

The minimum target sample size is 250 patients. Patient eligibility will be assessed at patient index date. Patients in Cohort 1 will be identified during a 15-month lookback period prior to the date of site initiation, and patients in Cohort 2 will be identified

PFIZER CONFIDENTIAL CT24-WI-GL03-RF03 2.0 Non-Interventional Statistical Analysis Plan 01-Jun-2020 Page 11 of 42 following the date of site initiation if the minimum target sample size for the study is not achieved from Cohort 1.

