#### Limitations and Bias

As this is a retrospective observational study and participant enrolment in the study will be done in a consecutive manner. This approach is associated with low possibility of bias and representativeness of the enrolled sample could be affected, if there is pattern observed among a particular age group or due to any season etc. In case such selection bias is observed, then additional stratification/ subgroup can be reported in the analysis, as required.

Since this study will involve collection of existing data from medical records, misclassification bias due to recording errors is possible. Medical records may not always be complete, the availability and quality/completeness of data may vary

> PFIZER CONFIDENTIAL CT24-WI-GL03-RF03 2.0 Non-Interventional Statistical Analysis Plan 01-Jun-2020 Page 23 of 42

considerably between different sites within KSA, and there may be abstraction errors and differences in reporting standards between the different sites.

Another limitation to be considered is the characteristics of the patient population to be included in the final analysis, which may potentially be biased based on the KSA national recommendations put in place for the management and treatment of COVID-19 during the observational period. This may affect the generalizability of findings from this study across different countries in the real-world setting.

At the patient-level, misclassification of drug exposure has to be considered. Medical records provide detailed information on patient demographics, clinical characteristics, and prescribed nirmatrelvir, ritonavir treatment, but may not contain information on the intended duration of use (days of supply) and may not contain accurate information on the actual treatment pattern of nirmatrelvir, ritonavir medications by the patient ie, patient adherence (if any).

COVID-19 outcomes are dependent on individuals seeking healthcare i.e., individual may have symptoms for long but if there is not an interaction with the health system, it will be unknown.

Number	Description					
Table shells for P	Table shells for Primary objectives					
Table shell 1	Summary of patient enrolment at Index date.					
Table shell 2	Summary of demographic characteristics of patients at Index date.					
Table shell 3	Summary of clinical characteristics of patients at Index date.					
Table shell 4	Summary of COVID-19 vaccination history of patients at Index date.					

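### The exploratory model of COVID-19-related hospitalisation has no site term and no planned output is by site, although both documents expect data completeness to vary between the three sites, so its pooled odds ratios are open to confounding by centre

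*SAP*

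**What the plan says.** Protocol 9.10 lists as a limitation that "the availability and quality/completeness of data may vary considerably between different sites within KSA". SAP 8 repeats it, saying that completeness may vary "considerably between different sites within KSA, and there may be abstraction errors and differences in reporting standards between the different sites".

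SAP 3.1.1 describes the setting: "In addition, these three healthcare centers have the same guidelines for treatment and management of patients with COVID-19". Both documents provide for a standardised eCRF. Protocol 9.10 adds completion guidelines, training, and quality metrics meant to identify sites with abstraction problems.

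SAP 4.2 states: "Exploratory stratifications will be conducted, as appropriate and where the sample size permits, to explore differences by" twelve listed variables, none of which is site. The table sets of SAP 7.3 items 1 and 2 use six strata each, again without site. No table title listed in SAP 9 mentions site.

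SAP 7.3 item 3 models COVID-19-related hospitalisation at the index date. Patients not hospitalised and patients hospitalised for other reasons are both coded 0. The covariates are age group, gender, BMI category, smoking, "Pre-existing comorbidities (Yes/No, Reference group: No", previous infection and vaccination. Univariate models are fitted for these only. Those significant at two-sided 0.05 enter the multivariable model, together with covariates judged clinically significant.

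**The concern.** Data from three record systems are pooled, and the plan itself expects those records to differ in completeness. Site can then act on both sides of the regression. Comorbidity, BMI, smoking and vaccination are read from site records. The outcome depends on the cause recorded for an admission, for which SAP Annex 1 gives two labels, where available, and no criteria for assigning them.

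If a covariate is recorded more often at a site that also has more admissions labelled as COVID-19 related, the pooled model shows an association that exists in no single site. Because univariate significance governs entry, such an artefact can bring a variable into the multivariable model. A site pattern in the opposite direction can keep a real factor out. Without any by-site output, a reader cannot tell which applies.

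**Working it through.** **What the documents supply.** The SAP gives a target of about 250: "the minimum target sample size for the study is approximately 250 evaluable patients across 3 sites in KSA". The protocol gives "a planned minimum total sample size of 500 patients for this study" and says that "power calculations are not applicable". Alpha is 0.05, two-sided. There are no site-level rates of hospitalisation or of covariate recording and no effect size, so there is no planned figure to reproduce. Everything below rests on assumed rates, and the range is shown.

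**Set-up.** Three sites of equal size. At site i, a proportion h_i is hospitalised for COVID-19 and a proportion c_i has a comorbidity recorded. The two are independent within each site, so the true within-site odds ratio is 1.

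**Formulas.** The pooled cells are averages over sites: a = mean(h·c), b = mean((1−h)·c), e = mean(h·(1−c)), d = mean((1−h)·(1−c)). The pooled OR is a·d/(b·e). The standard error of ln OR is √(Σ 1/(N·cell)). With z = ln OR/SE, the chance of p < 0.05 is Φ(z−1.96) + Φ(−z−1.96).

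**Worked case (moderate).** Take h = 10/20/30% and c = 50/65/80%.
- a = (0.05+0.13+0.24)/3 = 0.14
- b = (0.45+0.52+0.56)/3 = 0.51
- e = (0.05+0.07+0.06)/3 = 0.06
- d = (0.45+0.28+0.14)/3 = 0.29
- OR = 0.14×0.29/(0.51×0.06) = 1.33
- At N = 250 the expected counts are 35, 127.5, 15 and 72.5, so SE = 0.342, z = 0.83, and the false-positive rate is 13%.

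**All cases.** Where a range is given, it spans the formula and 1,000 simulated logistic fits per setting.

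| Assumed site differences | h (%) | c (%) | Pooled OR | False positives, N = 250 | N = 500 |
|---|---|---|---|---|---|
| Hospitalisation only | 10/20/40 | 65/65/65 | 1.00 | about 5% | about 5% |
| Recording only | 20/20/20 | 50/65/85 | 1.00 | about 5% | 5–7% |
| Mild, both | 15/20/25 | 60/65/70 | 1.05 | about 5% | about 5% |
| Moderate, both | 10/20/30 | 50/65/80 | 1.33 | about 13% | 18–22% |
| Strong, both | 10/20/50 | 50/65/90 | 2.04 | 56–59% | 85–89% |
| Strong, opposite | 50/20/10 | 50/65/90 | 0.56 | about 50% | 77–79% |

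With two site indicators in the simulated models, the false-positive rate is 4–6% in every row and at both sizes.

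**Cost in parameters.** Four age bands (3), gender (1), BMI (3), smoking (2), comorbidity (1), previous infection (1) and vaccination (1) make 12. Site makes 14. At N = 250:
- assumed 20% hospitalised (50 events): 50/12 = 4.2 falls to 50/14 = 3.6
- assumed 40% (100 events): 100/12 = 8.3 falls to 100/14 = 7.1

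If the 18–29 reference group named in SAP 7.3 is a separate fifth age band, the counts are 13 and 15, and at 50 events the fall is from 3.8 to 3.3.

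**The case against.** The strongest reply is that the plan already controls site differences at source, through shared treatment guidelines, one eCRF, completion instructions, training and data-quality metrics by site. SAP 8 also allows extra strata if selection bias is seen. The model is labelled exploratory, and the bias may be nil: it needs site to be linked to both the covariate and the outcome, and mild differences give only 1.05.

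Much of this stands. It limits the likely size and the weight of the point. It does not remove it. Common guidelines address practice rather than recording. The collection measures reduce differences, yet both documents still list such differences as a limitation. The optional strata depend on someone noticing a pattern, the examples given are age group and season, and no planned output would show a site pattern.

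It is also fair to say that the study's objectives describe the pooled treated population. Pooled percentages are therefore the intended result, and by-site columns throughout the descriptive tables would be a reporting preference.

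A reader might infer that one centre prescribes mainly on wards and another in clinics. The documents do not say so, and their only statement on centre practice is that guidelines are shared. A reader might also infer that no table shows site at all. The shells are in a separate spreadsheet that is not among the documents, and shell 1, on enrolment, could hold site counts. Only the listed titles and planned strata can be judged.

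**Conclusion.** The point holds for the exploratory hospitalisation model. Its pooled odds ratios are open to confounding by centre, and the plan has no term or table that would reveal or remove it. On assumed rates, with three equal sites and no true association, the pooled odds ratio runs from 0.56 to 2.04, and it is 1.00 when sites differ in only one of the two quantities. The documents cannot place this study within that range.

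Two stronger readings are not supported. One is that the odds ratios will be wrong: the calculation shows only that they can be. The other is that reporting standards are expected to vary considerably: both documents attach that degree to availability and quality or completeness, and say only that reporting standards may differ.

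**What to change.** In SAP 7.3 item 3, add site as a forced fixed effect (three levels, 2 df) in the multivariable model. Three sites are too few for a reliable random effect. Keep the univariate models as crude estimates, as the SAP defines them, and show the site-adjusted estimate for each covariate beside the crude one. Add one table by site with enrolment, missingness of the model covariates, and COVID-19-related hospitalisation at index.

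No new data are needed, since the contributing site is inherent in the collection. The cost is one table, one extra column of estimates and two parameters in a model that may already have few events, so other terms may need limiting. Site adjustment removes confounding by centre. It does not correct misclassified or missing values within a site, and the SAP should say so when it interprets the odds ratios.
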